13.2.7.4 Serious Adverse Event

If any AEs are serious, as defined by the FDA Code of Federal Regulations (CFR), Title 21, special procedures will be followed. All SAEs will be reported to the Sponsor via fax or e-mail within one working day of becoming aware of the event, whether or not the serious events are deemed drug-related. All serious event reporting will adhere to 21 CFR 312.32 for Investigational New Drugs (IND) and to the Guidance for Industry and Investigators: Safety Reporting Requirements for INDs and BA/BE, dated December 2012. The institutional review board (IRB) will be notified of the Alert Reports as per FDA regulations.

A SAE is any AE or suspected adverse reaction that in the view of either the PI (or designee) or Sponsor, results in any of the following outcomes: Death, a life-threatening AE, inpatient hospitalization or prolongation of existing hospitalization, a persistent or significant incapacity or disability, or a congenital anomaly/birth defect. Important medical events that may not result in death, be life-threatening, or require hospitalization may be considered serious when, based upon appropriate medical judgment, they may jeopardize the patient or subject and may require medical or surgical intervention to prevent one of the outcomes

listed in the above definition. Examples of such medical events include allergic bronchospasm requiring intensive treatment in an emergency room or at home, blood dyscrasias or convulsions that do not result in inpatient hospitalization, or the development of drug dependency or drug abuse.

Life-threatening is defined as an AE or suspected adverse reaction that in the view of the PI (or designee) or Sponsor, its occurrence places the patient or subject at immediate risk of death. It does not include an AE or suspected adverse reaction that, had it occurred in a more severe form, might have caused death.

All SAEs occurring from the signing of consent through 7 days after the last dose of study drug (omeprazole or LOXO-292, whichever comes last) must be reported on a SAE Report Form provided by LOXO Oncology and sent by fax or e-mail to the Sponsor listed in [Section 3](#) within 24 hours of the knowledge of the occurrence.

When using the SAE efax ([contact]) a cover page including study identification number and study drug product (i.e., LOXO-292) is required. Alternatively, an email can be sent to [contact].

The PI is not obligated to actively seek information regarding the occurrence of new SAEs beginning after the 7-day postdose period. However, if the PI learns of such an SAE, and that event is deemed relevant to the use of study drug, he/she should promptly document and report the event.

The PI will be requested to supply detailed information as well as follow-up regarding the SAE. Although not considered an AE per se, the Sponsor must be notified of any subject or subject's partner who becomes pregnant during the study at any time between the start of screening until 90 days after the last administration of study drug.

13.3 Pharmacokinetic Assessments

13.3.1 Blood Sampling and Processing

For all subjects, blood samples for the determination of LOXO-292 will be collected in blood collection tubes at scheduled time points as delineated in the Study Events Flow Chart ([Section 6](#)).

Instruction for blood sampling, collection, processing, and sample shipment will be provided separately.

13.3.2 Plasma Pharmacokinetic Parameters

PK parameters for plasma LOXO-292 will be calculated as follows, as appropriate:

AUC0-t:	The area under the concentration-time curve, from time 0 to the last observed non-zero concentration, as calculated by the linear trapezoidal method.
AUC0-inf:	The area under the concentration-time curve from time 0 extrapolated to infinity. AUC0-inf is calculated as the sum of AUC0-t plus the ratio of the last measurable plasma concentration to the elimination rate constant.
AUC%extrap:	Percent of AUC0-inf extrapolated, represented as $(1 - AUC0-t/AUC0-inf) * 100$.
Cmax:	Maximum observed concentration.
CL/F:	Apparent total plasma clearance after oral (extravascular) administration, calculated as Dose/AUC0-inf.
Tmax:	Time to reach Cmax. If the maximum value occurs at more than one time point, Tmax is defined as the first time point with this value.
Kel:	Apparent first-order terminal elimination rate constant calculated from a semi-log plot of the plasma concentration versus time curve. The parameter will be calculated by linear least-squares regression analysis using the maximum number of points in the terminal log-linear phase (e.g., three or more non-zero plasma concentrations).
t _{1/2} :	Apparent first-order terminal elimination half-life will be calculated as $0.693/Kel$.

No value for Kel, AUC0-inf, CL/F, or t_{1/2} will be reported for cases that do not exhibit a terminal log-linear phase in the concentration-time profile.

No PK parameters will be calculated for subjects with 2 or fewer consecutive time points with detectable concentrations.

Individual and mean plasma concentration time curves (both linear and log-linear) will be included in the final report.

13.3.3 Analytical Method

Samples will be analyzed for plasma LOXO-292 using validated bioanalytical methods. Samples from subjects to be assayed are specified in [Section 14.2](#).

13.4 Blood Volume Drawn for Study Assessments

Table 3: Blood Volume during the Study

Sample Type	Number of Time Points	Approximate Volume per Time Point * (mL)	Approximate Sample Volume Over Course of Study (mL)
Screening laboratory safety tests (including hematology, serum chemistry, serology, and coagulation), FSH (for postmenopausal female subjects only) and serum pregnancy (for female subjects only).	1	16	16
On-study hematology, serum chemistry (this includes serum pregnancy for female subjects only when scheduled at the same time), coagulation	9	16	144
Blood for LOXO-292	78	4	312
Total Blood Volume (mL)→			472 **

* Represents the largest collection tube that may be used for this (a smaller tube may be used).

** If additional safety or PK analysis is necessary or if larger collection tubes are required to obtain sufficient plasma/serum for analysis, additional blood may be obtained (up to a maximum of 50 mL)

14 STATISTICAL CONSIDERATIONS

Data will be handled and processed according to Celerion Standard Operating Procedures, which are written based on the principles of GCP.

14.1 Sample Size Determination

CCI subjects are considered sufficient to evaluate the magnitude of the food effect and of a gastric pH change on the PK of LOXO-292.

14.2 Population for Analyses

PK Population: Plasma samples from all subjects will be assayed even if the subjects do not complete the study. All subjects who comply sufficiently with the protocol and display an evaluable PK profile (e.g., exposure to treatment, availability of measurements and absence of major protocol violations) will be included in the statistical analyses.

Safety Population: All subjects who received at least one dose of the study drug will be included in the safety evaluations.

14.3 Statistical Analyses

Detailed methodology for summary and statistical analyses of the data collected in this study will be documented in a Statistical Analysis Plan (SAP). The SAP will be prepared by Celerion and agreed upon with the Sponsor. This document may modify the plans outlined in the protocol; however, any major modifications of the primary endpoints definition and/or its analysis will also be reflected in a protocol amendment. Additional statistical analyses other than those described in this section may be performed if deemed appropriate.

14.3.1 Pharmacokinetic Analyses

14.3.1.1 Descriptive Statistics

Values will be calculated for the LOXO-292 plasma concentrations and the PK parameters listed in [Section 13.3.2](#) using appropriate summary statistics to be fully outlined in the SAP.

14.3.1.2 Analysis of Variance

An ANOVA will be performed on the ln-transformed AUC0-t, AUC0-inf, and Cmax. The ANOVA model will include sequence, treatment, and period as fixed effects, and subject nested within sequence as a random effect. The ANOVA will include calculation of LSMs as well as the difference between treatment LSMs.

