Subjects will be randomized to treatment sequences to minimize assignment bias. A crossover design is used to reduce the residual variability as every subject acts as their own control. The washout period between LOXO-292 doses is considered sufficient to prevent carryover effects of the treatments. However, as omeprazole may have a prolong effect on acid secretion due to the irreversible nature of omeprazole binding to H⁺/K⁺ ATPase pump, the omeprazole treatment portion will be conducted only in Period 3 and Period 4 to ensure the effect of food without a PPI can be assessed without confounding factors.

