10 STUDY DESIGN

10.1 Overall Study Design and Plan

This is an open-label, randomized, 4-treatment, crossover study.

CC1 [REDACTED] healthy, adult male and female subjects (women of non-childbearing potential only) will be enrolled. Every attempt will be made to enroll at least 3 subjects of each sex in the study.

Screening of subjects will occur within 28 days prior to the first dose.

Subjects will be randomized to one of four treatment sequences: ABCD, ABDC, BACD, and BADC. Every attempt will be made to include the same number of females in each sequence and the same number of males in each sequence.

On Day 1 of Periods 1 and 2, a single oral dose of LOXO-292 will be administered under fasted or fed conditions, according to the randomization schedule, followed by PK sampling for 168 hours.

In Periods 3 and 4, multiple oral doses of omeprazole will be administered once daily from Day -4 of Period 3 until Day 7 of Period 4, inclusive (for a total of 18 consecutive days) with a single oral dose of LOXO-292 coadministered on Day 1 of each period under fasted or fed conditions, according to the randomization schedule. Pharmacokinetic sampling for LOXO-292 will be taken for 168 hours following LOXO-292 dosing on Day 1 in each period.

There will be a washout period of 7 days between LOXO-292 dose in Period 1 and LOXO-292 dose in Period 2 and between the LOXO-292 dose in Period 2 and the first dose of omeprazole in Period 3. There will be no washout between Periods 3 and 4 omeprazole doses although the LOXO-292 doses will be separated by a 7-day washout.

Safety will be monitored throughout the study by repeated clinical and laboratory evaluations.

Subjects may be replaced at the discretion of the Sponsor.

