14.3.1.3 Ratios and Confidence Intervals

Ratios of LSMs will be calculated using the exponentiation of the difference between treatment LSMs from the analyses on the ln-transformed AUC0-t, AUC0-inf, and Cmax. These ratios will be expressed as a percentage relative to the appropriate reference treatment.

Consistent with the two one-sided test [Schuirmann, 1987], 90% CIs for the ratios will be derived by exponentiation of the CIs obtained for the difference between treatment LSMS resulting from the analyses on the ln-transformed AUC0-t, AUC0-inf, and Cmax. The CIs will be expressed as a percentage relative to the appropriate reference treatment.

The comparisons of interest are as follows:

- Treatment B compared with Treatment A (food effect)
- Treatment C compared with Treatment A (gastric pH change by PPI under fasted)
- Treatment D compared with Treatment B (gastric pH change by PPI under fed)
- Treatment D compared with Treatment C (food effect under PPI)

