## 1. INTRODUCTION

The following statistical analysis plan (SAP) provides the framework for the summarization of the data from study LOXO-RET-18015. The SAP may change due to unforeseen circumstances. Any changes made from the planned analysis within the protocol or after the locking of the database will be documented in the clinical study report (CSR). The section referred to as Table Shells within this SAP describes the traceability of the tables, figures, and listings (TFLs) back to the data. Note that the header for this page will be the one used for the main body of the CSR.

Any additional exploratory analyses not addressed within this SAP and/or driven by the data, or requested by Loxo Oncology, Inc., will be considered out of scope and will be described in the CSR as needed.

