## 6.7 Statistical Analysis of PK Parameters

A comparison of ln-transformed PK parameters (AUC0-t, AUC0-inf, and Cmax) will be made to evaluate the effect of:

- Food on the single-dose administration of LOXO-292 (Treatment B Versus Treatment A);
- The effect of gastric pH change by multiple-dose administrations of omeprazole on the single-dose administration of LOXO-292 under fasted conditions (Treatment C Versus Treatment A);

- The effect of gastric pH change by multiple-dose administrations of omeprazole on the single-dose administration of LOXO-292 under fed conditions (Treatment D Versus Treatment B);
- The effect of food on the single-dose administration of LOXO-292 under gastric pH change by multiple-dose administrations of omeprazole (Treatment D Versus Treatment C)

by performing an analysis of variance (ANOVA) model using PROC MIXED in SAS®.

The ANOVA model will include sequence and treatment as the fixed effects and

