# 8. SUMMARY OF CHANGES FROM PROTOCOL-PLANNED ANALYSIS

The analyses described in this SAP are aligned with those analyses described in the protocol.

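### The protocol's period term leaves the omeprazole comparisons and all treatment means non-estimable; the SAP's readable model drops period without declaring the change, so the randomised food contrasts lose period adjustment

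*Protocol*

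**What the plan says.** Protocol 10.1: "Subjects will be randomized to one of four treatment sequences: ABCD, ABDC, BACD, and BADC". Protocol 8.2.1 explains why C and D always come last: "the omeprazole treatment portion will be conducted only in Period 3 and Period 4", so that food can first be studied free of residual acid suppression.

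Protocol 14.3.1.2 gives one model for ln AUC0-t, ln AUC0-inf and ln Cmax: "The ANOVA model will include sequence, treatment, and period as fixed effects, and subject nested within sequence as a random effect". It adds: "The ANOVA will include calculation of LSMs as well as the difference between treatment LSMs". Section 14.3.1.3 takes four ratios with 90% CIs from that model: B/A and D/C (food), C/A and D/B (omeprazole, fasted and fed). The two omeprazole ratios are primary objective 2 in Protocol 9.1.

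The readable part of SAP 6.7 says: "The ANOVA model will include sequence and treatment as the fixed effects and". The sentence stops there. The SAP shells for Tables 11-3 and 14.2.1.10 print geometric LSMs for each treatment and an intra-subject CV% from the residual variance. SAP 8 says: "The analyses described in this SAP are aligned with those analyses described in the protocol".

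**The concern.** The protocol's primary model cannot produce what the protocol asks of it. Run as written, it gives no estimate for primary objective 2 and nothing for the LSM columns.

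The SAP's readable model avoids that by leaving period out altogether, and this has two consequences. The order of A and B, and of C and D, was randomised, so B/A and D/C could be adjusted for period but are not. And C/A and D/B become computable only by assuming that average period effects are the same in Periods 1-2 as in Periods 3-4. The readable text states neither the change nor that assumption.

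**Working it through.** **Inputs.** Sequences ABCD, ABDC, BACD, BADC (Protocol 10.1). A and B in Periods 1-2, C and D in Periods 3-4 (Protocol 12.1). Model terms from Protocol 14.3.1.2 and SAP 6.7. The sample size is redacted, and no SD or period effect is given. Assumed: n = 20 in equal sequences, within-subject log SD *s* of 0.15 to 0.30, and a log shift *d* of 0.05 to 0.20 between the two periods of a stage (a stage being Periods 1-2 or 3-4). Widening at n = 16 or 24 agrees within 0.4 percentage points.

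**1. Estimability, protocol model.** In every record, (A or B) = (Period 1 or 2). Add any δ to the effects of Periods 3 and 4 and subtract δ from the effects of C and D: every fitted mean is unchanged. Under that move:

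- C-A and D-B each change by -δ: not estimable.
- An LSM averages the four period effects equally, and that average rises by δ/2. LSMs of A and B change by +δ/2, and those of C and D by -δ + δ/2 = -δ/2: not estimable.
- B-A and D-C do not change: estimable.

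Rank check:

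| Fixed effects | Columns | Rank | Estimable |
|---|---|---|---|
| Sequence, treatment, 4-level period | 1+4+4+4 = 13 | 9 (10 without the alias) | B-A and D-C only; no LSM |
| Sequence, treatment | 1+4+4 = 9 | 7 | All four contrasts, all LSMs |
| Sequence, treatment, two centred covariates | 1+4+4+2 = 11 | 9 | All four contrasts, all LSMs |

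Unequal sequence sizes, or about 10% of records missing, leave the protocol model's pattern for the four contrasts unchanged.

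**2. Cost of dropping period, balanced data.** B/A and D/C stay unbiased. In each stage a shift *d* adds n·d²/2 to the residual sum of squares, which has 3(n-1) = 57 df. With *k* stages affected,

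width ratio = √[1 + k·n·d² / (6(n-1)·s²)].

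Example, s = 0.20, d = 0.10, k = 2: 2×20×0.01 / (6×19×0.04) = 0.4/4.56 = 0.0877; √1.0877 = 1.043. With k = 1 it is about 1.022. Simulation (40,000 trials per cell) gives 1.043 and 1.021, identical for all four contrasts because the residual is pooled.

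| CI widening at d = 0.05 / 0.10 / 0.15 / 0.20 | Shift in both stages | Shift in one stage |
|---|---|---|
| s = 0.15 | 1.9 / 7.5 / 16 / 27% | 1.0 / 3.8 / 8.4 / 14.5% |
| s = 0.20 | 1.1 / 4.3 / 9.4 / 16% | 0.5 / 2.2 / 4.8 / 8.4% |
| s = 0.30 | 0.5 / 1.9 / 4.3 / 7.5% | 0.2 / 1.0 / 2.2 / 3.8% |

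At s = 0.20 the reported intra-subject CV% rises from 20.2 to 20.4 / 21.1 / 22.1 / 23.6 (both stages) or 20.3 / 20.6 / 21.2 / 21.9 (one).

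**3. Unbalanced data.** Without period, an 11:9 split of AB to BA biases ln(B/A) by d×(11-9)/20 = 0.1d, that is 0.5 / 1.0 / 1.5% for d = 0.05 / 0.10 / 0.15. The centred model gives zero. SAP 4.1 (emesis) and SAP 6.5 (predose concentration above 5% of Cmax) can remove single treatments or periods; how often is not documented.

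**4. C/A and D/B.** With balanced data both carry mean(Periods 3, 4) minus mean(Periods 1, 2) of the period effects, with or without the centred covariates. A shift of 0.10 in Period 2 only gives 0 - 0.05 = -0.05 log (-4.9%). A trend of 0.05 per period gives 0.125 - 0.025 = +0.10 log (+10.5%). At s = 0.20 the 90% CI then covers about 80% and 53% respectively. This comes from the fixed order, not from the choice of model.

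**The case against.** The algebra is not in dispute. The case against concerns weight.

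- **The SAP sentence is cut off.** Visible 6.7 also lacks the random effect, LSMs and CIs, which the shells require, so text is plainly missing and may mention period. This stands as a limit on the SAP half. The fixed-effects list does read as closed, so omission is the likelier reading. On any reading something must change: a class period term brings back the non-estimability, any other coding departs from the protocol, and no period at all is an undeclared change.
- **The SAP may modify the protocol, and its readable model already estimates everything.** Protocol 14.3 allows this, and SAP 1 promises: "Any changes made from the planned analysis within the protocol or after the locking of the database will be documented" in the study report. So the missing estimate for objective 2 is a defect of the protocol text, not of the analysis likely to be run. This stands. It does not make the SAP 8 statement correct.
- **The precision loss is hypothetical and conservative.** Continuous confinement, standardised meals and 7-day washouts limit period shifts. No passage supports the 27% cell, and no margin or decision rule is visible for wider intervals to affect. This stands.
- **The largest biases belong to the fixed order.** Correct: they support disclosure and add nothing to the case for changing the model.
- **A new model would come late.** SAP 3 describes an open-label study in the past tense. The documents do not say whether concentration data had been seen, so the declaration should give the timing.

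**Conclusion.** The concern holds. That the protocol model cannot estimate C/A, D/B or any treatment LSM is a matter of design algebra and needs no assumed figure, only the natural reading of Periods 1 to 4 as one class factor. The undeclared removal of period rests on the readable part of SAP 6.7.

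The practical cost to B/A and D/C is small: no bias with balanced data, and CIs 2 to 4% wider at SD 0.20 and a 0.10 shift. These sizes depend on an assumed n, SD and shift. C/A and D/B rest on an unstated assumption of equal average period effects in the two stages, which no model can check or remove. No changed conclusion is shown. The text should still be corrected, because the stated primary model and the SAP's claim of alignment cannot both stand.

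**What to change.** **SAP 6.7.** Replace period with two numeric covariates: x1 = -1/2 in Period 1, +1/2 in Period 2, otherwise 0; x2 = -1/2 in Period 3, +1/2 in Period 4, otherwise 0. Keep sequence, treatment and random subject within sequence, and evaluate LSMs at x1 = x2 = 0. Do not use a class term for period nested in stage; it stays aliased. Separate A/B and C/D models with period would serve the food contrasts but are not equivalent: 18 rather than 55 residual df, t(0.95) 1.734 against 1.673 (+3.6%), and expected CI width 2.7% greater than with the centred model.

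**SAP 8.** Declare the change, its reason and its timing. State that C/A and D/B are fixed-order comparisons that assume equal average period effects in Periods 1-2 and 3-4, and that the covariates do not remove this assumption.

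**Study report and protocol.** Record the change in the study report. Amend Protocol 14.3.1.2 only if the change is judged major under Protocol 14.3; such an amendment would be retrospective. If the unseen rest of SAP 6.7 already handles period in an estimable way, only SAP 8 and the protocol text need reconciling.

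**Cost.** A few sentences, two derived variables and a study-report note. Residual df fall from 57 to 55, which raises the t-multiplier from 1.672 to 1.673 (0.06%). No new data.

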14.3.1.3 Ratios and Confidence Intervals

Ratios of LSMs will be calculated using the exponentiation of the difference between treatment LSMs from the analyses on the ln-transformed AUC0-t, AUC0-inf, and Cmax. These ratios will be expressed as a percentage relative to the appropriate reference treatment.

Consistent with the two one-sided test [Schuirmann, 1987], 90% CIs for the ratios will be derived by exponentiation of the CIs obtained for the difference between treatment LSMS resulting from the analyses on the ln-transformed AUC0-t, AUC0-inf, and Cmax. The CIs will be expressed as a percentage relative to the appropriate reference treatment.

The comparisons of interest are as follows:

- Treatment B compared with Treatment A (food effect)
- Treatment C compared with Treatment A (gastric pH change by PPI under fasted)
- Treatment D compared with Treatment B (gastric pH change by PPI under fed)
- Treatment D compared with Treatment C (food effect under PPI)

14.3.2 Safety Analyses

All safety data will be populated in the individual CRFs. All safety data will be listed by subjects.

Dosing dates and times will be listed by subject.

AEs will be coded using the Medical Dictionary for Regulatory Activities (MedDRA[®]) and summarized by treatment for the number of subjects reporting the treatment emergent adverse event (TEAE) and the number of TEAEs reported. A by-subject AE data listing including verbatim term, coded term, treatment, severity, and relationship to treatment will be provided.

Safety data including ECGs, physical examinations, vital signs assessments, clinical laboratory results, will be summarized by treatment and point of time of collection.

Descriptive statistics using appropriate summary statistics will be calculated for quantitative safety data as well as for the difference to baseline, when appropriate.

Concomitant medications will be listed by subject and coded using the WHO drug dictionary. Medical history will be listed by subject.

